4.2.10.2 Derivations

Patients who did not experience chronic target PN pain palliation will be censored at the end date of the last non-missing cycle as defined in Section [4.2.9.1](#), that is, at the last cycle with non-missing average chronic target PN pain intensity score and “eligible” pain medication data. Patients with no post-baseline average cycle chronic target PN pain palliation scores will be excluded from the analysis.

Only PAINS-pNF chronic target PN pain scores and pain medication data during the randomised period (i.e., up to and including Cycle 12) will be considered.

4.2.10.3 Intercurrent Events

Follow the same approach as outlined for chronic target PN pain palliation in Section [4.2.9.3](#).

4.2.10.4 Handling of Dropouts and Missing Data

Not applicable.

4.2.10.5 Primary Analysis of TPP

KM curves will be used to estimate the distribution of TPP. The 25th, 50th, and 75th percentiles of KM estimates will be used to estimate TPP. A two-sided 95% CI will be provided for these estimates. TPP distributions between the two study intervention arms will be compared using a log-rank test stratified by geographical region.

A KM plot will be produced.

If there is an incident of interruption of randomised intervention that results in cycle outcomes omitted from the analysis for any patient, the KM analysis will be performed with interval censoring using PROC ICLIFETEST (SAS procedure) and a Cox proportional hazard regression model will be performed using PROC ICPHREG (SAS procedure). If there is no such incident, the SAS procedures PROC LIFETEST and PROC PHREG will be used for the analyses. The Cox proportional hazards model will include treatment and geographical region as fixed effects and baseline chronic target PN pain intensity score and baseline chronic PN pain medication modified WHO analgesic ladder score as covariates.

Separate analyses will be performed for each of the time-to-event definition (defined in Section 4.2.10.1).

The analysis will be performed on a subset of the Pain FAS population with an evaluable baseline assessment and at least one evaluable post-baseline cycle, that is, both average cycle chronic target PN pain intensity score (same definition as 1st key secondary endpoint; refer to Section 4.2.2.1.2) and chronic PN pain medication score (see Section 4.2.9.4 for missing pain medication derivation).

4.2.11 PN Pain Medication, Change in PN Pain Medication and PN Pain Medication Decrease During the Randomised Period

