			C1 D8	C1 D28	C2 D28	C4 D28	C6 D28	C8 D28	C10 D28	C12 D28	C16 D28	C20 D28	C24 D28 w	C30 b D28 onwards			
Study Day	Day – 28 to Day – 1	Day 1	Day 8	Day 28	Day 56	Day 112	Day 168	Day 224	Day 280	Day 336	Day 448	Day 560	Day 672				
Window (days)			Day 4-14	± 3	± 3	± 7	± 7	± 7	± 7	± 7	± 7	± 7	± 7	± 7	+ 7	+ 7	
PK blood samples u			X														8.5.1
AEs v	X	X	←	=====	=====	=====	=====	=====	=====	=====	=====	=====	=====	→			8.3
Concomitant medication/ procedures	X	X	←	=====	=====	=====	=====	=====	=====	=====	=====	=====	=====	=====	→		6.5

a The 28-day screening period will commence on the date the ‘Screening Visit’ transaction is registered in IRT system. Visit schedule should always be calculated in relation to C1D1. Visits should not be skipped or overwritten in IRT. If a visit (+ visit window) is missed, the visit should be completed as the earliest opportunity. If there is a long gap between the scheduled and actual visit, please check with global study team how visits are to be recorded.

b From Cycle 30 onwards, for all participants remaining on study intervention, assessments will be performed every 6 cycles with the exception of ophthalmic assessments (see footnote l) and pregnancy assessments (see footnote m).

c The EoT visit will be performed for participants who permanently discontinue study intervention for any reason (except for death, lost to follow-up or withdrawal of consent). The EoT visit should be performed as soon as possible after the decision to discontinue treatment permanently has been made. If EoT is >30 days after last treatment dose, then the EoT assessments can also function as the 30-Day Safety follow-up visit.

d Screening tests should be performed within 28 days before the first administration of study intervention, unless otherwise indicated. Written informed consent and any locally required privacy act document authorisation must be obtained prior to performing any protocol-specific procedures, including screening/baseline evaluations.

e Every effort should be made to minimise the time between randomisation and starting treatment (maximum interval of 3 business days of randomisation).

f Assessment of baseline disease characteristics includes documenting location of the target and non-target PN (if applicable) and any PN-related symptoms and results of any previous genetic testing for NF1.

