4.2.9.4 Handling of Dropouts and Missing Data

Missing components required for the determination of chronic target PN pain palliation may result if there is:

- Missing average cycle chronic PN pain intensity score for a specific cycle, that is, patients does not have at least 4 out of 7 PAINS-pNF chronic target PN pain intensity scores in at least 3 non-overlapping 7-day periods (same definition as for 1st key secondary endpoint; see Section 4.2.2.1.2);

and/or

- Missing pain medication:
 - 1) For eDiary, missing chronic PN pain medication for all days* (i.e., 28-day cycle) in that specific cycle.
 - 2) For investigator assessment, missing eCRF investigator assessment of analgesic use at that specific cycle.

*For the purposes of this analysis, pain medication data are considered missing *for a day* if the gatekeeper item “Did you take any medication for your usual (chronic) tumour pain from the time you went to bed last night until now (including overnight)?” is “yes” but no pain medications have been entered or the gatekeeper item is missing.

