4.2.10 Time to Chronic Target PN Pain Palliation During the Randomised Period

4.2.10.1 Definition

Time to chronic target PN pain palliation (TTPP) is defined as time to first chronic target PN pain palliation.

The date of the last day of the cycle will be used for calculating the time to event; therefore, time to event will be measured in months. TTPP will be defined as the duration of time in months from randomisation to the date of the last day of the first cycle where chronic target PN pain palliation is achieved.

Chronic target PN pain palliation is defined in Section [4.2.9.1](#).

The main definitions for chronic target PN pain palliation are proposed to be the primary, sensitivity 1, and sensitivity 2 definitions, resulting in 3 time-to-event endpoints. However, other definitions in [Table 14](#) might be considered, especially should the psychometric analysis demonstrate a clinically meaningful within-patient change different than the pre-specified value of 2.

The randomised period is defined in Section [3.3.2.2](#).

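### SAP 4.2.10.5 uses interval-censored methods for time to pain palliation only when a treatment interruption removes a cycle, never for diary or medication gaps, so the hazard ratio can be biased in either direction

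*SAP*

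**What the plan says.** - **Event time.** SAP 4.2.10.1 runs the clock from randomisation to the end of the first palliated cycle: "The date of the last day of the cycle will be used for calculating the time to event". Only data "up to and including Cycle 12" count (4.2.10.2).
- **Censoring.** SAP 4.2.10.2: "Patients who did not experience chronic target PN pain palliation will be censored at the end date of the last non-missing cycle". This covers patients who never reach palliation. It is silent on an unobserved cycle that precedes an observed event.
- **Method.** SAP 4.2.10.5 uses PROC ICLIFETEST and PROC ICPHREG under one condition: "If there is an incident of interruption of randomised intervention that results in cycle outcomes omitted from the analysis for any patient". Otherwise, "If there is no such incident, the SAS procedures PROC LIFETEST and PROC PHREG will be used for the analyses". No tie method is given.
- **Missing data.** SAP 4.2.10.4 reads only "Not applicable". Yet SAP 4.2.9.4 lists ways in which palliation status is missing: "Missing average cycle chronic PN pain intensity score for a specific cycle", or missing medication data for that cycle.
- **Gaps are expected.** SAP 4.2.2.1.6.1 gives a broken eDiary as an example of a missing cycle, and allows for 10% to 35% missing data when it imputes the pain scores that feed this endpoint.

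**The concern.** An unobserved cycle carries the same information whatever caused it. Take a patient who is not palliated in cycle 2, has no outcome in cycle 3 and is palliated in cycle 4. The first palliated cycle was 3 or 4. If cycle 3 was lost to a treatment interruption, the SAP treats the time as interval-censored. If it was lost to a diary failure, the SAP dates the event to the end of cycle 4 as exact, possibly 28 days late.

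The switch also depends on the data in an odd way. One interruption in one patient changes the method for the whole trial; any number of diary gaps changes nothing. Once triggered, the rule does not say how the interval limits are formed, whether diary gaps then count, or what replaces the log-rank test stratified by region. The endpoint table in SAP 4.2 does not mention the switch.

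Event times also cluster near at most 12 cycle ends, so ties matter and their handling is left open. At stake is the hazard ratio of a comparative secondary endpoint.

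**Working it through.** **The plan's own figure.** The documents give no sample size, event count or hazard ratio for this endpoint. The Pain FAS is sized on the first key secondary endpoint (SAP 3.4): difference 2, SD 2.8, two-sided alpha 0.05, power 90%.

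- n per arm = 2 × (1.960 + 1.282)² × 2.8² / 2² = 41.2, so 42. With 20% dropout, 42 / 0.8 = 52.5, so 53 per arm and 106 in total. This reproduces.

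**Anchor for the hazard ratio.** Assume a placebo mean change of 0 (not in the documents) and a normal distribution.

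- Placebo: P(improvement of at least 2) = Φ(-2/2.8) = 23.8%. Selumetinib (mean change -2): 50%.
- HR = ln(1 - 0.50) / ln(1 - 0.238) = 2.55. Values above 1 favour selumetinib.

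**Simulation.** 53 per arm, 12 cycles, 20% dropout at a random cycle. The hazard is flat, or front-loaded because Protocol 4.2 reports paediatric pain improvement after 2 cycles. Each cycle is missing independently; the SAP's 10% and 35% serve as assumed rates. Palliation persists once reached unless stated. The interval-censored fit is a grouped proportional hazards likelihood: with L the last evaluable non-palliated cycle and R the first evaluable palliated cycle, an event contributes S(L) - S(R) and a censored patient S(L).

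Median hazard ratios, true value 2.55 (300 runs for flat hazard with equal missingness, 800 otherwise):

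| Placebo palliation, hazard | Missing placebo / selumetinib | Breslow | Efron | Interval-censored |
|---|---|---|---|---|
| 23.8%, flat | 0 / 0 | 2.52 | 2.56 | 2.58 |
| 23.8%, front | 0 / 0 | 2.45 | 2.55 | 2.57 |
| 50%, front | 0 / 0 | 2.25 | 2.51 | 2.55 |
| 23.8%, flat | 35% / 35% | 2.49 | 2.53 | 2.54 |
| 23.8%, front | 35% / 35% | 2.44 | 2.51 | 2.54 |
| 50%, flat | 35% / 35% | 2.40 | 2.49 | 2.53 |
| 50%, front | 35% / 35% | 2.34 | 2.54 | 2.61 |
| 23.8%, front | 10% / 35% | 2.43 | 2.52 | 2.61 |
| 50%, front | 10% / 35% | 2.20 | 2.37 | 2.63 |
| 23.8%, front | 35% / 10% | 2.50 | 2.62 | 2.56 |
| 50%, flat | 35% / 10% | 2.55 | 2.67 | 2.61 |
| 50%, front, palliation present in 30% of later cycles | 35% / 35% | 2.23 | 2.37 | 2.40 |

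**Reading the results.**

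1. *Ties.* In the heaviest case Breslow gives 2.25/2.55 - 1 = -12%. At the anchor it is -1% to -4%. Efron stays within 2% without missing cycles.
2. *Equal missingness of 35%.* Efron is 2.48 to 2.55 across all runs, 0 to 3% low (the 2.48 is from a 300-run repeat of the 50% front-loaded case).
3. *Unequal missingness.* More gaps on selumetinib: down to 2.37/2.55 - 1 = -7%. More gaps on placebo: up to 2.67/2.55 - 1 = +5%. The interval-censored fit stays between 2.56 and 2.63 in the same runs.
4. *Transient palliation.* The interval-censored fit gives 2.40, little better than Efron at 2.37.
5. *No effect (HR 1).* Rejection was 4 to 6% with either tie method.

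**Simulation error.** With about 38 events, SE(log HR) ≈ √(4/38) = 0.32, so the median of 800 runs has an error near 1.25 × 0.32/√800 = 1.4%, and of 300 runs about 2.3%. The equal-missingness shift is close to that noise. Methods were compared on the same simulated data, so differences between columns are firmer than the levels.

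**The case against.** **The stronger reading.** A reader might infer that the hazard ratio will be attenuated. The documents do not support that. Equal missingness barely moves it, and unequal missingness can inflate it. The tie effect needs a Breslow-type approximation together with many early events; the SAP names PROC PHREG but not how it will handle ties. It also needs near-exact ties. Time runs from randomisation, and dosing may follow within a "maximum interval of 3 business days of randomisation" (Protocol 1.3), so some ties break. Spreading event times by 0 to 4 days moved the heaviest-tie Breslow result from 2.25 to 2.46.

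**Gaps may be rare.** A cycle score needs only 4 days in each of 3 weeks, and Protocol 8.1.8.9 flags diary compliance at or below 85%. The 10% to 35% figure is stated for imputing another endpoint. No document suggests a difference between arms. This stands as a limit on the size, not on the inconsistency.

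**The consequence is small.** The endpoint is outside the multiple testing procedure (SAP 3.3.7), and palliation is also analysed cycle by cycle (SAP 4.2.9.5). That stands.

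**The remedy is imperfect.** If palliation comes and goes, a first episode hidden in a gap can be followed by a non-palliated cycle, which puts the lower limit too late. That also stands.

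None of this explains why one cause of a missing cycle changes the method for everyone and the others change nothing.

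**Conclusion.** The rule is inconsistent and incomplete, and the point is minor. Cycles lost to diary or medication gaps are never interval-censored in their own right, and a later event is then dated as exact. The resulting bias has no fixed direction: about 0 to 3% with equal missingness and roughly -7% to +5% with 35% against 10%. A separate attenuation of up to about 12% is possible if a Breslow-type approximation meets many early, closely tied events.

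These sizes rest on assumptions outside the documents: a placebo mean change of 0 for the anchor, 50% placebo palliation for the extreme cases, the hazard shapes, independent missing cycles, and the SAP's 10% to 35% applied to cycles. A claim of inflated type I error would not be supported either: the endpoint carries no confirmatory alpha, and rejection under no effect stayed near 5%.

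**What to change.** Amend SAP 4.2.10 as follows.

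- Pre-specify one method whatever the reason a cycle is missing: interval-censored proportional hazards, or a discrete-time complementary log-log model.
- Place each event between the last evaluable non-palliated cycle and the first evaluable palliated cycle.
- Name the matching generalised log-rank test, stratified by geographical region, and align the endpoint table in SAP 4.2.
- If PROC PHREG is kept as a sensitivity analysis, specify Efron or exact ties.
- Replace the entry in 4.2.10.4 with this rule, citing the missing-cycle definitions in 4.2.9.4.

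The cost is SAP wording and slightly more complex fitting; the interval-censored procedures are already named. The SAP should also say that bias is not fully removed if palliation is transient.

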4.2.11.1 Definition

See Section 3.3.8 for definitions.

4.2.11.2 Derivations

For both spike and chronic PN pain medication, the analgesic ladder class and the strongest analgesic ladder score for each cycle will be derived following the scoring algorithm presented in Section 3.3.8. For chronic PN pain, changes from baseline (Increased/Decreased/No Change) will also be derived as outlined in Section 3.3.8.

At each cycle, a binary variable will be derived, set to 1 if a decrease in chronic PN pain medication is observed as per definition in Section 3.3.8 and 0 otherwise. A sensitivity definition of this binary endpoint is derived using the secondary definition of decrease from baseline as assessed by the investigator when the reason for the decrease in analgesic requirement is PN pain.

4.2.11.3 Intercurrent Events

The intercurrent event strategy for the chronic target PN pain palliation is described in [Table 16](#)

Table 16: Intercurrent Event Strategy for Decrease in Pain Medication

Intercurrent event	Strategy	Details
Changes to patients' chronic PN pain medication	N/A	Included in endpoint definition.
Randomised study intervention discontinuation and early crossover from placebo to selumetinib in patients with documented progression on imaging (as determined by ICR per REiNS criteria)	While on-treatment strategy	The strongest analgesic ladder scores following randomised study intervention discontinuation will not be included.
Target PN resection	Treatment policy strategy	The strongest analgesic ladder scores after a target PN surgical resection will be included in the analysis.

ICR, independent central review; N/A, not applicable; PN, Plexiform Neurofibroma; REiNS, Response Evaluation in Neurofibromatosis and Schwannomatosis.

4.2.11.4 Handling of Dropouts and Missing Data

For the chronic PN pain medication based on the eDiary, the strongest class of pain medications reported over the 28 days of each cycle will be based on observed scores, that is, days with missing information will be ignored in the derivation.

For purposes of the analysis of decrease in pain medication, 1) if the pain medication data provide sufficient evidence to rule out a decrease for a cycle (see Section 4.2.9.2), that cycle is considered not to have missing pain medication data; 2) if, due to missing *daily*

pain medication data as defined in Section 4.2.9.4, the cycle does not provide sufficient evidence to rule out either an increase or a decrease in pain medication for a cycle, that cycle will be considered to have missing pain medication data.

For the investigator's assessment of change in pain medication, analyses will be based on observed data.

4.2.11.5 Primary Analysis of Pain Medication

The pain medication decrease during the randomised period will be analysed using a random-effect logistic regression model including treatment, geographical region, and cycle number as fixed effects; baseline chronic PN pain medication score as covariates; and the following interaction terms: treatment-by-cycle number and baseline chronic PN pain medication score-by-cycle number.

A random intercept will also be included to account for variability between patients. An unstructured covariance matrix will be used to allow for unequal treatment variance and to model the correlation between different treatment measurements within the same subject. If the fit of the unstructured covariance structure fails to converge, the following covariance structures will be used in order until convergence is reached: toeplitz with heterogeneity, autoregressive with heterogeneity, toeplitz, autoregressive, and compound symmetry. All main effects and the interaction terms will remain in the model regardless of significance.

The results of the analysis are presented in terms of an odds ratio (selumetinib versus placebo) together with its 95% CI and p-value at each cycle (estimated using the treatment-by-cycle interaction coefficient) and overall, over the randomised period (based on the treatment coefficient). For each treatment arm, the odds will be presented along with the number of non-missing observations used in the estimation (n), the observed number and percentage of responders, and the corresponding 95% CIs. The analysis will be performed on a subset of the FAS population with an evaluable baseline and at least one post-baseline chronic PN pain medication score available. Data collected during the randomised period (see Section 3.3.2.2) adhering to the intercurrent event strategy (refer to Section 4.2.11.3) are included.

This analysis will be repeated using the sensitivity definition outlined in Section 4.2.11.2. For the sensitivity using investigator assessment of analgesic use, the random-effect logistic regression model will include treatment, geographical region, and cycle number as fixed effects; baseline chronic PN pain medication score as covariate; and the following interaction terms: treatment-by-cycle number and baseline chronic target PN pain medication score-by-cycle number.

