Added eCDF plot for the 1 st key secondary endpoint as a supplementary analysis	21Dec2023	The empirical cumulative distribution function of change from baseline by study intervention arm will be plotted at each cycle during the randomised period for the Pain FAS (Section 4.2.2.1.7)	N/A	Requested by the FDA for the validation of the PAINS-pNF questionnaire
PFS, TTR, and TTP derived from randomisation date	21Dec2023	To align with the start of the randomised period and with company standards, efficacy time-to-events are derived from the randomisation date and not from the date of first dose.	N/A	To align with company standards
Clarification that box plots of interocular pressure should be done by eye	21Dec2023	2 sets of box plots in the same output, one for the left eye and one for the right eye	N/A	Clarification on derivation
Change in the derivation of partial volumes for following DCOs	21Dec2023	In order to keep responses reported at DCO1 unchanged for patients with partial volumes after DCO1 (similar for DCO2)	N/A	To keep consistency with interim and primary analyses
Added PROMIS total score	21Dec2023	To have a total score to help the interpretation of physical function results	N/A	To have a physical function summary

CATEGORY Change refers to:	Date	Description of change	In line with CSP?	Rationale
Updated PK Analysis Set definition	21Dec2023	To match the protocol	Yes	To match the protocol
Removed EQ5D plots and clog log plot for TPP	21Dec2023	Not necessary for interpretability of results	N/A	Unnecessary for interpretability of results
Added summaries of PGIS and PGIC	12 Jan 2024	Added shift table and summary statistics of the distribution of score by treatment over time	No	PGIS and PGIC are collected in the study to support the psychometric validation of the PAINS-pNF questionnaire. However, following a request by the clinical and HrQoL teams, these analyses have also been included as additional exploratory clinical outcome assessments for the CSR.
Writing and formatting QC	18 Jan 2024	Writing and formatting QC Checks by Synchrogenix	N/A	As per company standards
Stratification factors	25 Apr 2024	Average baseline chronic target PN pain group missing as stratification factor from the primary analysis for the following endpoints: PlexiQoL (Section 4.2.2.2.5); PII-pNF pain interference total score (Section 4.2.12.5); PROMIS (Section 4.2.13.5); PedsQL (Section 4.2.14.5); EQ-5D-5L (Section 4.2.15.5).	No	Omitted from model in error

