It is estimated that approximately 212 adult patients will be enrolled at approximately 46 sites across 13 countries to achieve approximately 146 patients randomised to study intervention. Patients will be randomised 1:1 to receive selumetinib or placebo (i.e. 73 patients per arm). Randomisation will be stratified at the central level by average baseline PAin INTensity Scale for Plexiform Neurofibroma (PAINS-pNF) chronic target PN pain score (< 3 and \geq 3) and geographical region (Europe, China, Japan, and Rest of World). A blocked randomisation will be generated, and randomisation will be balanced within the IRT at the central level. The number of patients randomised will be capped at approximately 106 patients with an average baseline PAINS-pNF chronic target PN pain score \geq 3 and approximately 40 patients with an average baseline PAINS-pNF chronic target PN pain score < 3. Patients randomised to selumetinib will receive selumetinib 25 mg/m² orally twice daily (bid) (based on body surface area [BSA], capped at 50 mg bid when BSA is \geq 1.9 m²) in 28-day cycles until a selumetinib discontinuation criterion is met. Patients randomised to placebo will receive placebo orally bid and will receive selumetinib treatment after the end of Cycle 12. Selumetinib capsules will be administered using BSA-based dosing. If it is anticipated that 20% or more of patients (across blinded study intervention groups) withdraw prior to the end of Cycle 16 for reasons other than progression, then recruitment rates notwithstanding, enrolment will continue to randomise at least 50% of the total number of dropout patients to ensure that the primary endpoint is adequately powered.

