2 CHANGES TO PROTOCOL PLANNED ANALYSES

- The split of the safety analysis set (SAF) into the Randomised Period SAF and the On-Selumetinib SAF is not listed in protocol.
- Patient Global Impression of Severity (PGIS) and Patient Global Impression of Change (PGIC) are collected in the study to support the psychometric validation of the PAINS-pNF questionnaire. However, following a request by the clinical and health related quality of life (HrQoL) teams, summary statistics of PGIS and PGIC by treatment over time have been included as additional exploratory clinical outcome assessments (COAs) for the CSR.
- The stratification factor ‘average baseline chronic target PN pain group’ has been omitted from primary analysis model in error in the CSP for the following endpoints: PlexiQoL (Section 4.2.2.2.5); PII-pNF pain interference total score (Section 4.2.12.5); PROMIS (Section 4.2.13.5); PedsQL (Section 4.2.14.5); EQ-5D-5L (Section 4.2.15.5).
- Subgroup analyses by baseline PAINS-pNF chronic target PN score group for PII-pNF, PROMIS, PedsQL and EQ-5D-5L will not be performed but these analyses will be supplementarily run on the set of patients with a baseline PAINS-pNF chronic target PN pain intensity score ≥ 3 (pain FAS).
- The primary endpoint (ORR by end of Cycle 16) and related supplementary endpoints (Target PN volumes and BOR) will be analyzed in the FAS (i.e. ITT population) and not on the Measurable PN FAS defined in CSP, which requires participants to have a measurable target PN at baseline per ICR, following FDA feedback on SAP version 3. Subsequently, the definition of the following analysis sets have changed to remove the requirement of having a measurable target PN at baseline per ICR: selumetinib FAS, extended selumetinib FAS, fed measurable FAS.

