4.2.17.4 Primary Analysis of PAINS-pNF Spike Target PN Pain Intensity

The primary analysis for PAINS-pNF spike target PN pain intensity score will mirror the primary analysis of the 2nd key secondary endpoint, as described in Section [4.2.2.5](#), that is, the maximum score during the randomised period will be compared between arms using an MMRM model with treatment and geographical region as factors as well as baseline spike pain intensity score as a covariate and baseline spike pain intensity score-by-cycle and treatment-by-cycle as interactions. The LS mean (95% CI) in each study intervention arm as well as the treatment difference and p-value will be presented at each cycle and

overall, in the randomised period. A plot of the LS means accompanied by the 95% CI will be produced.

The analysis will be performed on the FAS population with a baseline score and at least one post-baseline assessment for spike target PN pain intensity.

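### Two FAS models, decrease in pain medication (SAP 4.2.11.5) and spike pain (SAP 4.2.17.4), still leave out the baseline-pain stratification factor that the SAP restored for five other endpoints; the effect is modest, and 4.2.17.4 contradicts itself

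*SAP*

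**What the plan says.** SAP 1.1 sets out the design: "Randomisation will be stratified at the central level by average baseline PAin INTensity Scale for Plexiform Neurofibroma (PAINS-pNF) chronic target PN pain score", split at 3, and by geographical region. The caps give unequal strata: "The number of patients randomised will be capped at approximately 106 patients with an average baseline PAINS-pNF chronic target PN pain score" of 3 or more, and "approximately 40 patients with an average baseline PAINS-pNF chronic target PN pain score < 3".

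SAP Section 2 states that the pain-group factor "has been omitted from primary analysis model in error in the CSP for the following endpoints", and names PlexiQoL, PII-pNF, PROMIS, PedsQL and EQ-5D-5L. The amendment history entry of 25 April 2024 gives the same reason: "Omitted from model in error". The five model sections (4.2.2.2.5, 4.2.12.5, 4.2.13.5, 4.2.14.5, 4.2.15.5) now list it. The FAS ANCOVA for best percentage change in target PN volume (4.2.8.4) includes it as well.

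Two further comparative models are fitted in the FAS:

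- Decrease in pain medication, 4.2.11.5 (secondary): a "random-effect logistic regression model including treatment, geographical region, and cycle number as fixed effects; baseline chronic PN pain medication score as covariates", with treatment-by-cycle and baseline-score-by-cycle interactions and a random intercept. The investigator-assessed version has the same terms.
- Spike pain, 4.2.17.4 (exploratory): said to mirror 4.2.2.2.5, and then spelled out as an "MMRM model with treatment and geographical region as factors as well as baseline spike pain intensity score as a covariate", with two interactions by cycle. The spike-pain row of the Section 4.2 endpoint table also names region and no pain group.

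Neither endpoint appears in the Section 2 list, and no reason is given for treating them differently.

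**The concern.** A factor used to stratify randomisation normally belongs in the analysis model. Stratification balances the arms on that factor, and a model that ignores it does not credit the balance: in a linear model the reported standard error is too large whenever the factor is prognostic. The sponsor has accepted this principle by calling the same omission an error elsewhere. Baseline chronic pain is plausibly related to both spike pain and changes in analgesics, and neither model carries the pain group or the continuous baseline chronic pain score.

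Section 4.2.17.4 has a second problem. A programmer who follows its cross-reference fits the pain group; one who follows its listed terms, or the endpoint table, does not. A pre-specified analysis should not allow both.

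**Working it through.** **Which models are affected.** Each comparative regression model in SAP 4.2 was compared with the two stratification factors.

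| Model | Population | Region | Pain group |
|---|---|---|---|
| PlexiQoL, PII-pNF, PROMIS, PedsQL, EQ-5D-5L | FAS subset | yes | yes (corrected) |
| Best % change in PN volume | FAS | yes | yes |
| Decrease in pain medication, both versions | FAS subset | yes | no |
| Spike pain | FAS with baseline and post-baseline score | yes | no in the listed terms; yes through the cross-reference |
| Chronic pain intensity, palliation, time to palliation | Pain FAS | yes | not needed: all patients are ≥3, and the continuous baseline score is in the model |

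The gap is therefore two endpoints. Each of the two models leaves out one of the two stratification factors, not both.

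**Linear model (spike pain, one visit).** The documents do not give the prognostic strength of the pain group, so it is assumed. Let R² be the share of residual variance it explains beyond the listed covariates.

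CI width with the factor / width without = √(1 − R²)

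- R² = 0.02: √0.98 = 0.990, so the CI without the factor is 1/0.990 = 1.010 times as wide.
- R² = 0.10: √0.90 = 0.949, so it is 1/0.949 = 1.054 times as wide.

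The same can be expressed as a difference of d residual SDs between the pain groups. With p = 106/146 = 0.726, p(1 − p) = 0.199, and SE inflation = √(1 + 0.199 d²):

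| d (assumed) | SE inflation | True two-sided alpha at nominal 0.05 | Power, if 80% when adjusted |
|---|---|---|---|
| 0.25 | 1.006 | 0.049 | 79.7% |
| 0.50 | 1.025 | 0.045 | 78.6% |
| 0.75 | 1.054 | 0.039 | 76.9% |
| 1.00 | 1.095 | 0.032 | 74.4% |

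R² = 0.02 corresponds to d of about 0.32, and R² = 0.10 to d of about 0.75. A 6,000-run ANCOVA simulation with 53/53 and 20/20 patients per stratum agrees: at d = 1.0, rejection under the null was 0.036 without the factor and 0.048 with it, and power was 73.9% against 78.9%.

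**Logistic model (medication decrease).** In a plain logistic model, leaving out a prognostic factor moves the odds ratio towards 1. For a true conditional OR of 2, a group OR of 2 to 5 and a placebo rate of 10–30%, the OR without the factor is 1.99 to 1.89. But 4.2.11.5 specifies a random intercept. A random-intercept logistic model without the pain group was fitted to exact population data (true OR 2; strata 106:40; group OR 2 or 5; placebo rate 10% or 30% in the <3 stratum; intercept SD 1 or 2; 6 repeats; all assumed). The fitted OR was 1.999 to 2.002 throughout. The omitted factor went into the intercept SD, which rose from 1.00 to 1.26 in the largest case. The unstructured covariance that 4.2.11.5 also mentions was not modelled.

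**Cycle main effect in 4.2.17.4.** For 2 arms and 12 cycles as class variables, the design with treatment and treatment-by-cycle has rank 24; adding cycle leaves it at 24. The per-cycle treatment differences are the same either way.

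**The case against.** The strongest case on the other side is that little is at stake. Neither endpoint is in the multiple testing procedure (SAP 3.3.7), balanced stratified randomisation leaves the linear estimate unbiased, and the error in the standard error is conservative. All of that stands.

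It can also be said that spike pain is already covered, because 4.2.17.4 points to a model containing the pain group. This stands only in part: the explicit list and the endpoint table say otherwise, so the text has to be reconciled.

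The Pain FAS repeat in 4.2.11.6 is a weaker answer. It covers pain medication, not spike pain, and it shows the ≥3 stratum alone without adjusting the FAS estimate.

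A further objection is that the <3 stratum may contribute little information. It is 40/146 = 27% of those randomised, but it includes patients with no chronic pain. A patient at ladder score 0 cannot decrease, cycles with no chronic medication recorded are set to missing (3.3.8), and spike cycles with a maximum of 0 are excluded (4.2.17.2). This stands as a caution: the informative share is probably below 27%, though the documents do not give it, and an extra term in the logistic model could cause separation or non-convergence.

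Three stronger readings are tempting, and none is supported:

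- A reader might infer that the medication odds ratio is pulled towards 1. That holds for a plain logistic model, but the random intercept specified here largely absorbs an omitted patient-level factor.
- A reader might infer that the endpoints closest to pain are the ones left unadjusted. PII-pNF pain interference does include the pain group, and the chronic-pain analyses use the baseline score within a single stratum.
- A reader might infer that the unlisted cycle main effect damages the spike-pain model. It leaves the per-cycle contrasts unchanged.

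**Conclusion.** The point holds as an incomplete correction and an internal contradiction. The SAP identifies the missing pain group as an error, restores it for five FAS endpoints, and leaves it out of two other FAS models without giving a reason. Section 4.2.17.4 supports two different models.

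The numerical effect is modest. For spike pain, the CI is about 1–5% too wide if the pain group explains an assumed 2–10% of residual variance, with a slightly conservative test. For medication decrease, no material bias in the odds ratio is shown under the random-intercept model. These figures rest on the assumed prognostic strength and on the randomised 106:40 split, which may overstate the informative share of the <3 stratum. Confirmatory type I error is not affected. The case for the change is consistency and an unambiguous specification, at little cost.

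**What to change.** 1. In SAP 4.2.11.5, add average baseline chronic target PN pain group (<3, ≥3) as a fixed effect in the FAS model, in both the eDiary and the investigator-assessed versions.
2. In SAP 4.2.17.4, add the same fixed effect, so that the listed terms agree with 4.2.2.2.5. List cycle as a factor too, for consistency only.
3. Align the two rows of the Section 4.2 endpoint table, and extend the Section 2 bullet to these endpoints. If the factor is left out on purpose, state the reason instead.
4. For the logistic model, state in advance that the pain-group term is dropped if it causes separation or non-convergence, and say where in the existing covariance fallback sequence this step comes.

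The Pain FAS repeat needs no change, because the factor is constant there. The cost is a few lines of text and one model term. The small downside is the possible scarcity of medication decreases in the <3 stratum, which step 4 covers. The edit should be made before unblinding, since a covariate added afterwards would look data-driven.
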